### 6.2.1.2.3 Dose Limiting Toxicities

All toxicities will be graded using the Common Terminology Criteria for Adverse Events (CTCAE) version 4.0 (see [Appendix D](#)). The occurrence of any of the following toxicities during the DLT evaluation period will be considered a DLT, if judged by the investigator to be related to the administration of blinatumomab:

- Any treatment-related death
- Any treatment-related toxicity, regardless of grade, that leads to a subject's removal from the study by the investigator and/or sponsor
- Persistent CTCAE grade  $\geq 2$  non-hematologic adverse events related to blinatumomab that are deemed intolerable by the subject or the treating physician and that do not respond to appropriate medical management within 5 days and lead to treatment discontinuation will be considered DLTs
- Recurrent grade 2 seizures ie, brief generalized seizures
- All grade 3 and 4 adverse events and laboratory abnormalities, which occur during the SC administration portion of the treatment period and which, in the opinion of the investigator, are at least possibly related to the investigational drug, are considered as DLT with exceptions noted below:
  - Laboratory parameters of grade  $\geq 3$  that responds to intervention/treatment interruption and resolves to grade  $\leq 1$  within 7 days
  - **Grade 3 and 4 lymphopenia**
  - Grade 3 fever or infection
  - Grade  $\leq 3$  events of CRS or tumor lysis syndrome that responds to intervention/treatment interruption and resolves to grade  $\leq 1$  within 7 days
  - **Grade 3 neurologic events that respond to intervention/treatment interruption and resolves to grade  $\leq 1$  within 7 days**

Approved

### 6.2.1.3 Premedication With Dexamethasone for Blinatumomab Treatment

Mandatory premedication with dexamethasone is required before each cIV and SC treatment cycle and dose-step for the prevention of CRS events resulting from blinatumomab treatment:

- Dexamethasone 20 mg IV within **6 hours** before the start of infusion/first injection on cycle day 1.
- Dexamethasone 20 mg IV within **6 hours** before **each** dose-step
- **Dexamethasone premedication 20 mg IV within 6 hours prior to starting SC on Cycle 1 Day 22, and within 6 hours prior to resuming IV on Cycle 1 Day 29 is mandatory (in Cycle 1/Period 1).**
- Dexamethasone premedication will also be required before the restarting blinatumomab after a dose interruption due to an adverse event. See [Table 1](#) for details.

Approved

**Table 1. Dexamethasone Pre-dose Treatment and for Events**

Treatment Phase	Target Subject (route of administration)	Dexamethasone Dose	Comments
Pre-dose Dexamethasone Prior to Each Treatment Cycle / Dose-Step	All subjects	Dexamethasone 20 mg IV within 6 hours before the start of infusion/first injection in each treatment cycle, and within 6 hours before the dose-step	See Section 6.1
Cycle 1/Period 1 Day 22 prior to starting SC Cycle 1/Period 1 Day 29 prior to resuming cIV		Dexamethasone 20 mg IV within 6 hours prior to first SC dose Day 22 and within 6 hours prior to resuming cIV on Day 29	See Section 6.2.1.1.1
Infusion Interruption/Dose Modification Due to Adverse Event	Subjects with treatment interruption > 4 hours (cIV) Subjects with ≥ 2 missed doses on the q12h dosing regimen and ≥ 1 missed dose on the q24h, q48h, q72h, q96h, or q7d dosing regimen (SC)	Dexamethasone 20 mg IV within 6 hours before the restart of treatment	See Section 6.1 and 6.2.1.4.2
In case of signs of CRS	Subjects with signs of CRS (cIV or SC)	Dexamethasone at a dose maximum 3 × 8 mg/day for up to 3 days. Reduce step-wise over 4 days.	See Section 6.2.1.4.2
In case of Neurologic Events	Subjects with central nervous system -related adverse event (cIV or SC)	Dexamethasone at a maximum dose of 24 mg/day × 3 days maximum. Reduce step-wise over 4 days.	See Section 6.2.1.4.2

Abbreviations: cIV = continuous intravenous, CRS = cytokine release syndrome, IV = intravenous, q12h = every 12 hours; q24h = every 24 hours; **q48h = every 48 hours; q72h = every 72 hours; q96h = every 96 hours; q7d = every 7 days**; SC = subcutaneous

**6.2.1.4 Dosage Adjustments, Delays, Rules for Withholding or Restarting, Permanent Discontinuation**

**6.2.1.4.1 Interruption of Blinatumomab cIV Administration or Missed Doses During SC Administration**

If possible, during the cIV administration of blinatumomab administration should not be interrupted. In case of blinatumomab interruption because of any technical or logistic reason, the interruption should be as short as possible and blinatumomab treatment should continue at the earliest time possible. Any interruption longer than 1 hour should

Approved

be documented. If the interruption is longer than 4 hours, re-start of blinatumomab should be performed in the hospital, under the supervision of the investigator. The subject should be observed overnight for possible side effects after the re-start of the cIV or SC IP, in the hospital. Premedication dexamethasone should be administered as described in [Table 1](#).

In the event of drug interruptions of > 4 hours in the cIV infusion, or if  $\geq 2$  doses are missed in the q12h SC dosing schedule **or**  $\geq$  a single missed dose in the q24h, **q48h, q72h, q96h, or q7d** SC dosing schedule, the restart of IP should be performed in the hospital under the supervision of the investigator, with premedication dexamethasone as described in [Table 1](#). The subject should be observed overnight for possible side effects after the re-start of the cIV or SC IP.

#### **6.2.1.4.2 Interruption of Blinatumomab Treatment/Dose Modification Due to Adverse Events**

Common Terminology Criteria for Adverse Events (CTCAE) grade 4 non-laboratory adverse events at least possibly related to blinatumomab will require permanent discontinuation of blinatumomab. For all CTCAE  $\geq$  grade 3 laboratory events reflective of hepatotoxicity or CRS, refer to [Sections 6.3](#) and [Table 2](#), respectively, for specific guidance for the interruption and discontinuation of therapy. Subjects who have been dose reduced will have an option to receive the higher dose level once the adverse event has resolved to grade 1 or less for at least 7 days. For interruptions or dose modifications because of neurologic events as defined in [Appendix E](#) (refer to [Table 2](#)).

If the interruption after an adverse event lasts no longer than 7 days, the same cycle should be continued. An infusion interruption of more than 2 weeks because of an adverse event related to blinatumomab will lead to permanent discontinuation of treatment. The infusion duration before and after an interruption should total 7 days at each dose level for cIV run-in and **the SC** treatment duration should be a total of 5 days for **dose cohorts 1, 2, and 3 or for any additional cohorts at the SC dose and frequency determined by the DLRT during week 4** in Cycle 1/Period 1. **For** Cycle 1/Period 2 after a treatment interruption, treatment will resume on the same treatment day of the week that it was originally interrupted on (eg, if there was an interruption on day 3 of a cycle, day 3 of the cycle will be repeated with all applicable assessments at re-start).

For cIV infusion of IP, the lowest dose for restart is 9  $\mu\text{g}/\text{day}$  if last dose given was 9 or 28  $\mu\text{g}/\text{day}$ . The lowest dose for restart should be 28  $\mu\text{g}/\text{day}$  cIV infusion if the last dose

given was 112 µg/day cIV infusion. Restart following a dose interruption for cIV infusion and SC should be performed in the hospital, under supervision of the investigator and the subject should be hospitalized for 48 hours.

For a grade  $\geq$  3 neurologic adverse event occurring at **initial dosing of 9 µg/day cIV in Cycle 1/Period 1 or 9 µg/day SC equivalent in Cycle 1/Period 2**, permanently discontinue blinatumomab.

Administer premedication as described in [Table 1](#). The treatment time for each of the treatment cycles is approximately 6 weeks.

Restart cIV infusion should be performed with a 9/28/112 µg/day weekly dose escalation if last dose given was 9 or 28 µg/day. If last dose given was 112 µg/day restart should be performed with a 28/112 µg/day dose escalation (dose escalation 1 week after restart).

For SC dosing, the doses that have equivalent exposures to the cIV doses mentioned above should be used.

Restart and dose escalation for cIV infusion and SC should be performed in the hospital, under supervision of the investigator and the subject should be hospitalized for 48 hours.

In addition, to the events described above, the dose may be temporarily or permanently reduced to 9 µg/day cIV infusion (or the equivalent SC dose) if, by the investigator's judgment, it is necessary for safety reasons. After at least 7 days of dosing at 9 µg/day cIV infusion (or the equivalent SC dose), the dose may be increased to 28 µg/day cIV infusion (or the equivalent SC dose) or treatment may be continued at the dose of 9 µg/day cIV infusion (or the equivalent SC dose) after consultation with an Amgen medical monitor. Likewise, if an event occurred at a dose of 112 µg/day cIV infusion or the SC MTD, the dose may be temporarily or permanently reduced to 28 µg/day cIV infusion (or the equivalent SC dose) and may be increased to 112 µg/day cIV infusion (or SC MTD) following the same guidance as described above. This does not apply for neurologic events (refer to [Table 2](#)).

Detailed instructions for blinatumomab interruption and re-start instructions for CRS, neurotoxicity, hepatotoxicity, and other clinically relevant adverse events are detailed in [Table 2](#).

Approved

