#### **6.2.1.1.4 Blinatumomab Inpatient Dosing**

It is mandated in this study that subjects are hospitalized at least during the first 72 hours at the start of cIV infusion (Cycle 1/Period 1, Optional Cycle 2/Period 1, and **Optional Cycle 2/Period 2 if administered as a cIV infusion**) as well as after any additional dose-step. Hospitalization is also required during the first 48 hours after the return to cIV infusion after the SC dosing in Cycle 1/Period 1. Subjects will remain hospitalized during the entire SC administration dosing in Cycle 1/Period 1.

In Cycle 1/Period 2, **subjects are hospitalized: For subjects 1-5: day 1 until completion of the second MTD dose PK being finished. Sites where outpatient PK cannot be obtained, for the third MTD SC dose, the subject needs to be hospitalized until completion of the third MTD dose PK. Subjects 6-15: are hospitalized on days 1-8 (discharge 8 hours after day 8, 28 µg/day equivalent SC dose is administered) and readmitted to the hospital on day 12 (prior to first MTD SC dose) until 8 hours after the second MTD SC dose is administered. Sites where outpatient PK cannot be obtained, for third 28 ug/day equivalent SC dose and third MTD SC dose, the subject needs to be hospitalized until completion of the third MTD dose PK.**

In **Optional Cycle 2/Period 2, if given SC subjects are hospitalized on days 1-8 (discharge 8 hours after day 8, 28 µg/day equivalent SC dose is administered) and readmitted to the hospital on day 12 (prior to first MTD SC dose) until 8 hours after the second MTD SC dose is administered.** The infusion bags will be changed (**if IP is administered as a cIV infusion**) and SC injections administered by trained site nursing personnel. Close monitoring during the first 72 hours of treatment at each dose will be required because of the potential for adverse events.

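### Protocol 6.2.1.4.2 allows 48 hours in hospital for a cIV dose escalation after an adverse-event restart, against the 72-hour minimum that 6.2.1.1.4 mandates after any cIV dose-step

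*Protocol*

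**What the plan says.** Protocol Section 6.2.1.4.2 covers interruptions and dose changes caused by adverse events. A cIV subject goes back through 9/28/112 µg/day, described as a "weekly dose escalation if last dose given was 9 or 28" µg/day. A subject last dosed at 112 µg/day goes through 28/112, with "dose escalation 1 week after restart". The section then says: "Restart and dose escalation for cIV infusion and SC should be performed in the hospital". The same sentence goes on to fix the length of stay: "under supervision of the investigator and the subject should be hospitalized for 48 hours".

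Section 6.2.1.1.4 sets the general inpatient rule: "It is mandated in this study that subjects are hospitalized at least during the first 72 hours at the start of cIV infusion", in Cycle 1/Period 1 and in any optional Cycle 2 given as cIV, "as well as after any additional dose-step". It adds: "Close monitoring during the first 72 hours of treatment at each dose will be required". It names one shorter cIV stay: "Hospitalization is also required during the first 48 hours after the return to cIV infusion after the SC dosing" in Cycle 1/Period 1.

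The schedules agree with the general rule. Table 3 footnote e gives at least 72 hours after each cIV dose-step, and Table 7 footnote d gives at least 3 days. Section 6.2.1.1.1 and the Synopsis use the term dose-step for the cIV increases to 28 and 112 µg/day.

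**The concern.** Two operative rules give different minimum stays for the same event, a cIV escalation such as 28 to 112 µg/day. The shorter one applies to subjects who have just had an adverse event serious enough to interrupt treatment.

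A site working from 6.2.1.4.2 alone could discharge such a subject at 48 hours. Section 5 points readers to that section for adverse-event interruptions, so this is a realistic way to use the protocol. The site would then have departed from a mandated minimum set elsewhere in the same document.

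What is at stake is subject safety and protocol compliance, not inference.

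**Working it through.** There is no plan figure to reproduce. The check is a comparison of text, followed by one subtraction.

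**1. Does the 48-hour sentence govern escalation?** Yes. Section 6.2.1.4.2 has already set 48 hours for restart a few paragraphs earlier. The later sentence repeats that and adds dose escalation, directly after the 9/28/112 and 28/112 schedules. Escalation is its only new content.

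**2. Are those escalations dose-steps under 6.2.1.1.4?** Yes. They are the same increases, to 28 and to 112 µg/day, that the protocol labels dose-steps in the planned schedule.

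**3. Is there an exception?** None was found. Section 6.2.1.1.4 speaks of any additional step and sets a minimum. It states its one 48-hour stay explicitly. Section 6.2.1.4.2 neither cross-refers to it nor gives a reason for a shorter stay.

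**4. Size of the difference**
- Inputs: 72 h per step (6.2.1.1.4, Table 3 footnote e; Table 7 footnote d as 3 days) and 48 h per step (6.2.1.4.2).
- One step: 72 − 48 = 24 h.
- Two steps: 2 × 72 − 2 × 48 = 144 − 96 = 48 h.

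**5. Where it falls, by the restart rules in 6.2.1.4.2 and Table 2**

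| Grade 3 event during Cycle 1/Period 1 | cIV restart dose | Later cIV steps | First exposure to that cIV dose? | Difference |
|---|---|---|---|---|
| At 112 µg/day cIV, or in the SC week | 28 | to 112 | No | 24 h |
| At 28 µg/day in the run-in | 9 | to 28, to 112 | Yes for 112 | 48 h (24 h of it at first exposure) |
| CRS or another non-neurologic event at 9 µg/day in the run-in | 9 | to 28, to 112 | Yes for both | 48 h (all at first exposure) |

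A grade 3 neurologic event at the initial 9 µg/day dose leads to permanent discontinuation, so it produces no later step.

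**6. The resulting order.** In the last two rows, a subject with a recent grade 3 event would have a 48-hour stay at first exposure to 112 µg/day under 6.2.1.4.2. A subject with no such event would have at least 72 hours.

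**The case against.** The strongest reply is that the rules can be met together. Section 6.2.1.1.4 mandates a minimum, while 6.2.1.4.2 says what should be done and does not call 48 hours a maximum. A site that keeps the subject 72 hours breaches neither. This stands: early discharge happens only if a site reads 6.2.1.4.2 on its own.

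A second reply is that 6.2.1.4.2 is a deliberate, specific rule for re-escalation. For an event at 112 µg/day, the later step returns the subject to a dose already experienced, after a week at 28 µg/day without recurrence, and 48 hours could be a clinical choice. That is arguable for those cases. It does not explain the first-exposure steps, which the sentence also covers.

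Third, other safeguards remain:
- close monitoring for 72 hours at each dose, which is not expressly tied to inpatient status;
- dexamethasone before each dose-step;
- outpatient treatment only if the investigator judges the subject stable;
- 7 days without recurrence before escalation;
- permanent discontinuation if the grade 3 event recurs at the lower dose within 7 days of re-initiation.

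These reduce the consequence but do not reconcile the two durations.

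A reader might go further in three ways that the documents do not support.
- **The 48 hours for restart itself is also wrong.** The start of cIV in 6.2.1.1.4 can mean the start of a cycle, and that section itself uses 48 hours for the return to cIV after the SC week.
- **SC escalations fall short too.** The 72-hour dose-step stay is stated for cIV, and SC stays have their own rules.
- **The number of subjects affected can be projected from the Amendment 6 rationale.** It reports grade 3 neurotoxicity in 2 of 12 SC-treated subjects. That counts neurotoxicity, not restart escalations; it does not say that either subject went through one; and all 12 had reached SC, so subjects lost in the run-in are missing. Both events, one in the SC week and one at 112 µg/day cIV, belong to the one-step row above. No study-wide count of subjects or hours can be built on this.

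**Conclusion.** Wrong as written: an internal inconsistency in a safety rule. For a cIV escalation after an adverse-event restart, 6.2.1.4.2 gives 48 hours where 6.2.1.1.4 and both schedule footnotes require at least 72, a gap of 24 hours per step. It matters most for first exposures: to 112 µg/day after a grade 3 event at 28 µg/day in the run-in, and to 28 and 112 µg/day after grade 3 CRS or another non-neurologic grade 3 event at 9 µg/day.

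The conclusion rests on reading the post-restart increases as dose-steps, which the protocol's own usage supports, and on the absence of any stated exception. That the mismatch exists is clear. That the sponsor meant 72 hours for every re-exposure step is less certain. The documents give no sound basis for how many subjects would be affected. No sample size, DLT rule, DLT window or analysis changes.

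**What to change.** In Section 6.2.1.4.2, replace the sentence that joins restart and escalation with wording to this effect:

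*Restart of cIV or SC, and any SC escalation, takes place in hospital under the investigator's supervision, with a 48-hour stay. Each cIV escalation after a restart is a dose-step under Section 6.2.1.1.4 and requires a hospital stay of at least 72 hours.*

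If the sponsor does intend 48 hours for some re-exposure steps, it should instead write that as an explicit exception in 6.2.1.1.4, Table 3 footnote e and Table 7 footnote d, limited to doses the subject has already received.

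The cost of the first option is one wording edit and 24 more inpatient hours per affected cIV step for sites that would otherwise have discharged at 48 hours.

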**Table 2. Treatment Interruptions and Restart**

Toxicity	Grade	Instructions for Treatment Interruptions and Restart
Neurologic Events	Grade 3	
If grade 3 neurologic adverse event occurred at 9 µg/day cIV or 9 ug/day SC equivalent without prior dose escalation
 
 
Permanently discontinue blinatumomab
 
 
If grade 3 neurologic adverse event occurred during cIV infusion
 
 
Interrupt blinatumomab until ≤ grade 1 and administer corticosteroids (refer to Table 1)
 
A contrast-enhanced MRI of the brain should be performed before treatment may be resumed
 
Restart no less than 72 hours after the initial observation of the grade 3 event:
 
 
For cIV infusions:
 
 
○ If event occurred at 112 µg/day cIV infusion, resume cIV infusion at 28 µg/day
 
○ If event occurred at 28 µg/day cIV infusion: resume cIV infusion at 9 µg/day
 
○ Escalate up 1 dose level after 7 days if toxicity does not reoccur. Increase dose stepwise at 7-day intervals to 112 µg/day cIV infusion
 
 
For SC week 4 Period 1/Cycle 1
 
 
○ Resume at 28 µg/day cIV infusion.
 
○ Escalate up after 7 days if toxicity does not reoccur to 112 µg/day cIV infusion for 7 days.
 
○ Hold cIV infusion for 12 hours if toxicity did not reoccur
 
○ Resume with the day SC that toxicity occurred at the dose of that cohort (ie, if toxicity occurred on day 23 then resume SC on day 23 of cycle and repeat all labs that are written for this day on Schedule of Assessments).
 
 
For SC Period 2:
 
 
○ If event occurred at MTD SC, resume SC at 28 µg/day equivalent
 
○ If event occurred at 28 µg/day SC equivalent, resume SC at 9 µg/day SC equivalent
 
○ Escalate up 1 dose level after 7 days if toxicity does not reoccur. Increase dose stepwise at 7-day intervals to MTD SC
 
 
Permanently discontinue blinatumomab if:
 
 
Initial grade 3 event does not improve to grade ≤ 1 within 7 days, OR
 
Grade 3 event reoccurs at the lower dose level within 7 days of re-initiation, OR
 
Initial Grade 3 event occurred at dose of 9 µg/day cIV or SC equivalent 9 ug/day without out prior dose escalation
 


Approved

**Table 2. Treatment Interruptions and Restart**

Toxicity	Grade	Instructions for Treatment Interruptions and Restart
Neurologic Events (continued)	Grade 4	
 
• Permanently discontinue blinatumomab
 
 
Seizure
 
 
• Interrupt blinatumomab and administer corticosteroids (refer to Table 1) and anti-seizure medication according to local practice
 
• For restart, refer to grade 3 neurologic events above for dose level rules for re-instituting infusion
 
• Do not re-initiate blinatumomab until 7 days after the last seizure and after therapeutic levels of anti-seizure medication are likely to have been achieved
 
• Permanently discontinue blinatumomab if:               
 
○ A second seizure occurs with re-initiation of blinatumomab at any dose
 
 
 

Cytokine release syndrome	Grade 3	
 
• Interrupt blinatumomab until <math>\leq</math> grade 1 and administer corticosteroids (refer to Table 1).
 
• Restart no less than 72 hours after the initial observation of the grade 3 event at the following dose levels:                For cIV infusions:               
 
• If event occurred at 112 <math>\mu\text{g}/\text{day}</math>, resume cIV infusion at 28 <math>\mu\text{g}/\text{day}</math>
 
• If event occurred at dose of 9 <math>\mu\text{g}/\text{day}</math> or 28 <math>\mu\text{g}/\text{day}</math>, resume cIV infusion at 9 <math>\mu\text{g}/\text{day}</math>
 
• Escalate up 1 dose level after 7 days if toxicity does not reoccur. Increase dose stepwise at 7-day intervals to target dose of 112 <math>\mu\text{g}/\text{day}</math> if toxicity does not re-occur
 
               For SC week 4 Period 1/Cycle 1               
 
○ Resume at 28 <math>\mu\text{g}/\text{day}</math> cIV infusion.
 
○ Escalate up after 7 days if toxicity does not reoccur to 112 <math>\mu\text{g}/\text{day}</math> cIV infusion for 7 days.
 
○ Hold cIV infusion for 12 hours if toxicity did not reoccur
 
○ Resume with the day SC that toxicity occurred at the dose of that cohort (i.e if toxicity occurred on day 23 then resume SC on day 23 of cycle and repeat all labs that are written for this day on Schedule of Assessments).
 
               For Period 2 SC:               
 
○ If event occurred at MTD SC, resume at 28 <math>\mu\text{g}/\text{day}</math> SC equivalent
 
○ If event occurred at SC dose equivalent to 9 <math>\mu\text{g}/\text{day}</math> or 28 <math>\mu\text{g}/\text{day}</math>, resume SC at 9 <math>\mu\text{g}/\text{day}</math> SC equivalent
 
○ Escalate up 1 dose level after 7 days if toxicity does not reoccur. Increase dose stepwise at 7-day intervals to MTD SC if toxicity does not re-occur
 
 
 

Approved

Abbreviations defined on last page of the table.

